While existing psychological therapies are effective for addressing general psychological issues such as depression or anxiety, they often fall short in addressing the unique, multifaceted challenges faced by individuals with diabetes (Diribe et al., 2024). Diabetes introduces specific stressors, including the constant burden of self-management (Yu et al., 2020) (e.g., blood glucose monitoring, dietary restrictions), health anxiety, and societal stigma, which generic therapies may not fully tackle (Akshatha & Nayak, 2024 & Harvey, 2015) . A tailored psychosocial program is necessary because it integrates biological, psychological, and social factors(Kusnanto et al., 2018) into a holistic approach, as outlined by the Biopsychosocial Model (Amsah et al., 2022). For instance, it can combine medical care with emotional, and social support lead to reduction of diabetes distress, health anxiety and stigma, thus improving QOL and treatment adherence providing a more comprehensive solution. In essence, a tailored psycho-social program will fill the gaps left by existing therapies, offering a comprehensive, diabetes-specific approach that addresses the unique needs of individuals living with diabetes (Bajwa, 2024) (Cimo & . Dewa, 2025).

Objectives {7}

The current study is designed to measure the role of PSP with T2DM patients. There are following objectives of this current study, such as

- To investigate the impact of Psycho-Social Program (PSP) for reducing diabetes-related distress, ad depression among T2DM patients
- To investigate the impact of Psycho-Social Program (PSP) for reducing health anxiety and stigma among T2DM patients
- To investigate the impact of Psycho-Social Program (PSP) for improving quality of life, and treatment adherence among individuals with T2DM.

Hypothesis of the Study

After review of the literature, the following hypotheses such as;

- Psycho-social program (PSP) will play a significant role to reduce mental health problems among patients with T2DM.
- Psycho-social program (PSP) will play a significant role to reduce diabetes distress, among patients with T2DM.
- Psycho-social program (PSP) will play a significant role to reduce depression among patients with T2DM.
- Psycho-social program (PSP) will play a significant role to reduce health anxiety among patients with T2DM.
- Psycho-social program (PSP) will play a significant role to reduce stigma among patients with T2DM.

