- Psycho-social program (PSP) will play a significant role for enhancing quality of life, and treatment among individuals with T2DM

Trial design {8}

Randomized control trial design would be used in this study. It would be two arm study and there would be two groups an experimental and wait-list control group. Experimental group will receive intervention and another group would be placed in waitlist. In this research, parallel group design would be used. We will give treatment to all participants in a parallel way. Allocation ratio and framework would be equivalence i.e., treatment group and control group would be equal number of participants.

Methods: Participants, interventions and outcomes

Study setting {9}

Randomized control trial design would be used in this study to find out the impact of PSP for psychiatric comorbidity and adherence to treatment among patients with T2DM.

Participants

In this study, the participants would be patients diagnosed with type II diabetes mellitus. For this purpose, N=80 diabetic patients would be approached from different hospitals of Faisalabad. Sample would be comprised of male and female with type II diabetes mellitus. In order to collect the data for our study, purposive sampling technique would be used. Patient age range would be 30-40 years. Participants would be divided into two group each group will be comprised of n=40. One group will be experimental group and second group will be wait-list control group.

Eligibility criteria {10}

The patients diagnosed with Type II Diabetes Mellitus (T2DM) male and female participants aged 30-40 years will be included in our study. The participants from different hospitals or clinic of Faisalabad will be included in our study. The patient with Type 1 Diabetes Mellitus (T1DM) would be excluded from our study. The patient with other serious co-morbid medical illness such as cancer, heart problems, and stroke will be excluded from our study. The patient with physical disability would be excluded from our study.

Who will take informed consent? {26a}

Researcher will be taken consent from all of the participants through consent form.

Additional consent provisions for collection and use of participant data and biological specimens {26b}

Informed consent will be given and confidentially would be ensures. Researcher will guide the participant that their participation would be volunteer.

Interventions

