Initially researcher would take permission from hospital of Faisalabad and data would be collected from hospital. Informed consent would be given and confidentiality would be ensured. Structured interview would be performed, the first meeting with experimental and waitlist control group would be to explain the nature and purpose of this intervention. The first group will receive PSP and second group will not receive PSP. Total 6-8 structured sessions of PSP would be conducted by following the training modules of cognitive behavior therapy. After conducting interviews with the T2DM patient's one on one assessment thoroughly conducted on each patient who will receive cognitive behavior therapy to record their baseline score. Then sessions of PSP will be conducted with T2DM patients, each session will agenda session. The review of each session will be performed with the help of session record sheet. After the completion of intervention program the comparison of both groups will be recorded separately and then compare for findings the difference and to check the effects of the intervention.

Sequence generation {16a}

Initially researcher would take permission from hospital and data would be collected from hospital. Informed consent would be given and confidentiality would be ensured. Structured interview would be performed, the first meeting with experimental and waitlist control group would be to explain the nature and purpose of this intervention. The experimental group will receive PSP and control group will not receive PSP. Total 8 structured sessions of cognitive behavior therapy would be conducted by following the training modules of PSP. After conducting interviews with the patients on one assessment thoroughly conducted on each patient who will receive cognitive behavior therapy to record their baseline score. Then sessions of cognitive behavior therapy will be conducted with patient, each session will be agenda session. The review of each session will be performed with the help of session record sheet. After the completion of intervention program, the comparison of experimental and control groups will be recorded separately and then compare for findings the difference and to check the effects of the intervention.

Concealment mechanism {16b}

Intervention would be provided physically i.e., face to face interaction between researcher and participants.

Implementation {16c}

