Major focus was given to patients' level of motivation and attitude toward treatment. Participants would be given motivation by the therapist to be the part of study to achieve a better mental health and avoid the distress associated with their illness. The participants who will leave the study incomplete and would show less interest for being a part of study would be discontinuing the study. .

Data management {19}

Data manage on the SPSS. First, patient screen out and then select patient who meet inclusion criteria. Next step is baseline assessment to experimental and control group, and after that give PSP to the experimental group then comparison between experimental and control group. At last, compare the pre and post assessment of the patients through paired sample T-test.

Confidentiality {27}

Demographic sheet would be used to collect personal information of the participants. Confidentiality would be ensured to the client that their information would be used only for research purpose and would be kept in privacy.

Plans for collection, laboratory evaluation and storage of biological specimens for genetic or molecular analysis in this trial/future use {33}

N/A

Statistical methods

Statistical methods for primary and secondary outcomes {20a}

Statistical Analysis with descriptive statistics (M, SD, f), Chi-square statistics and t-test for matchable group characteristics, and repeated measures ANOVA for pre-and post-outcomes evaluation will be conducted. In this study sample sizes will be calculated using G-Power Software. All analyses will be conducted using SPSS-26.

Interim analyses {21b}

[name] play as an interim analysis. He provides guidelines about the study.

Methods for additional analyses (e.g. subgroup analyses) {20b}

Descriptive statistics (i.e., Mean, Standard Deviation, Frequencies etc) will be used to calculate demographic characteristics of the sample.

Methods in analysis to handle protocol non-adherence and any statistical methods to handle missing data {20c}

We will follow the expert opinion to handle any issues related to non-adherence and missing data in our data.

Plans to give access to the full protocol, participant level-data and statistical code {31c}

All statistical computation would be calculated by using SPSS 24.0.

Oversight and monitoring

Composition of the coordinating center and trial steering committee {5d}

The participants would be recruited from the hospital Faisalabad.

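### The only test that Data management {19} names is a within-patient paired t-test, which cannot compare PSP with wait-list; {20a} names a different analysis without a deciding term

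*Protocol*

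**What the plan says.** The protocol touches the outcome comparison in four places.

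- **Data management {19}** describes screening, baseline assessment and treatment: "after that give PSP to the experimental group then comparison between experimental and control group". No test is attached to that comparison. The section then closes with "At last, compare the pre and post assessment of the patients through paired sample T-test". It does not say which arm's patients, or whether both arms are pooled.
- **Statistical methods for primary and secondary outcomes {20a}** says "repeated measures ANOVA for pre-and post-outcomes evaluation will be conducted". It does not name arm as a factor or say which term decides. The t-test in this section has another job: "Chi-square statistics and t-test for matchable group characteristics".
- **Assignment of interventions: allocation** says "the comparison of both groups will be recorded separately and then compare for findings the difference", in order to check the effect of the intervention. Again no test is named.
- **Trial design {8}** says "Allocation ratio and framework would be equivalence i.e., treatment group and control group would be equal number of participants".

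The hypotheses are directional, for example "Psycho-social program (PSP) will play a significant role to reduce diabetes distress, among patients with T2DM". The design is a two-arm parallel trial against a wait-list, with 40 patients per arm.

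**The concern.** {19} and {20a} give different analyses of the same pre and post scores and do not say how the two relate. Someone writing the analysis from this text could not tell which result decides the trial.

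The choice matters because the two are not interchangeable. A paired test asks whether scores moved within the patients tested. Over the three to four months of treatment allotted to each patient, scores can move through regression to the mean, usual care or repeated questionnaires. The wait-list arm is there to remove exactly those influences, and a paired test does not use it as a comparator. If the paired result were reported as the efficacy finding, PSP would be credited with any improvement common to both arms. Nobody is blinded after assignment {17a} and all the outcome scales described in {18a} are questionnaires, so it is especially important to fix the deciding test beforehand.

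**Working it through.** **Inputs.** From the protocol: 40 patients per arm, two arms, a pre and a post score on each scale. The protocol gives no effect size, SD, alpha, power or pre-post correlation, so its total of 80 cannot be reproduced. Assumed here: two-sided alpha 0.05, SD 1 at both times, pre-post correlation r = 0.3, 0.5 or 0.7, no dropout.

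**Step 1: the paired test when PSP does nothing.** Let both arms improve by g. The SD of a patient's change is √(2(1−r)), so the noncentrality for n patients is g√n / √(2(1−r)), with n−1 degrees of freedom. For g = 0.3 and n = 40:

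| r | SD of change | noncentrality | PSP arm significant |
|---|---|---|---|
| 0.3 | 1.183 | 1.604 | 35% |
| 0.5 | 1.000 | 1.897 | 46% |
| 0.7 | 0.775 | 2.449 | 67% |

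If the test pools all 80 patients, which the wording of {19} allows, the rates are 61%, 76% and 93%. The result depends heavily on g. In the PSP arm, g = 0.2 gives 18%, 23% and 36%, and g = 0.5 gives 74%, 87% and 98%.

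A simulation of 20,000 trials at r = 0.5 and g = 0.3 agrees: 45.5% for the PSP arm and 75.7% pooled. A between-arm test of change in the same trials rejects 5.0% of the time, as it should.

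**Step 2: the valid between-arm tests.** With two time points and arm as a between-patient factor, the group-by-time test is the two-sample t-test on change, with variance 2(1−r) per patient. ANCOVA on the post score with baseline as covariate has variance 1−r². The ratio of the two is (1+r)/2, which is 0.65, 0.75 and 0.85 at the three correlations. For a true difference d = 0.5 the noncentrality is d√(40/2) divided by the relevant SD, with 78 degrees of freedom for change and 77 for ANCOVA:

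| r | change: SD, noncentrality | power, group-by-time | ANCOVA: SD, noncentrality | power, ANCOVA |
|---|---|---|---|---|
| 0.3 | 1.183, 1.890 | 46% | 0.954, 2.344 | 64% |
| 0.5 | 1.000, 2.236 | 60% | 0.866, 2.582 | 72% |
| 0.7 | 0.775, 2.887 | 81% | 0.714, 3.131 | 87% |

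A normal approximation gives values about one point higher (47/61/82% and 65/73/88%), with the same conclusion. Below r = 0.5 the change score is less precise than the post score alone, because 2(1−r) then exceeds 1.

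**The case against.** The strongest reply is that the protocol does plan to compare the arms. {19} states a between-arm comparison just before the paired test, and the allocation section ends in one. {19} is the data-management item, while {20a} is the item for outcome analysis and names an ANOVA. Naming the deciding term is often left to a statistical analysis plan, which is not shown here. All of this stands, and it limits the point. It does not remove the conflict between {19} and {20a}, nor the fact that no test is tied to the arm comparison.

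Several stronger readings are tempting but not supported:

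- *The ANOVA also fails to test superiority.* With arm as a factor, its group-by-time term is a valid test of the hypotheses. The fault is that neither arm nor the term is named. Reading the group main effect instead would cut power at d = 0.5 to between 22% and 28%, but nothing in the protocol says that anyone will.
- *The trial will call PSP effective if its arm is significant and wait-list is not.* The protocol states no such rule. The phrase about recording groups separately is ambiguous and ends in a comparison of groups.
- *An equivalence analysis is planned.* Trial design {8} explains the word in the same sentence as equal group sizes, and no margin appears anywhere. It is a misused term.
- *The baseline score is thrown away.* Both named analyses use it through the change from baseline. They use it less efficiently than ANCOVA does.

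**Conclusion.** The point holds in this form: the only test {19} names cannot support a claim that PSP is better than wait-list, and {19} and {20a} conflict without stating which one decides. If PSP had no effect and both arms improved by 0.3 SD, the paired test in the PSP arm would be significant in 35% to 67% of trials, against 5% for a proper between-arm test.

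Preferring ANCOVA to the group-by-time term is a gain in precision, not the correction of an invalid test. At d = 0.5 the gain is about 18 points of power at r = 0.3, 12 at r = 0.5 and 6 at r = 0.7. The exact percentages rest wholly on assumed values. What does not depend on them is that the paired test has no arm contrast and that its rejection rate exceeds 5% whenever both arms improve.

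**What to change.** 1. In {19} and {20a}, state the same efficacy test: for each scale, one between-arm comparison by ANCOVA of the post-test score on arm, with that scale's baseline score as covariate. Report the adjusted mean difference with a two-sided 95% confidence interval.
2. If the 6-month assessment mentioned under Provisions for post-trial care {30} is also to be analysed, use a baseline-constrained mixed model, since a single post-test ANCOVA does not cover a second follow-up.
3. If the authors keep the repeated-measures ANOVA, they should name arm as the between-patient factor and group-by-time as the deciding term, and accept the lower power.
4. Label within-arm paired tests as descriptive only.
5. In Trial design {8}, replace the framework word with: 1:1 allocation, superiority framework.

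The cost is wording only. The data are the same, SPSS fits ANCOVA, and the covariate costs one degree of freedom. The protocol places enrolment after trial registration and describes registration as still to come, so on its own account the text can be corrected before outcome data exist.

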Methods: we will conduct randomized control trial with pre- and post- baselines using reliable and validated tools such as DDS, PHQ-9, SHAI, DSAS, MSPSS, DQOL and GMAS. Total N=80 diabetic patients would be divided into experimental n=40 and waitlist n=40 participants. Participants would be taken from different hospitals of the Faisalabad. Patient's age range would be 30-40 years. Peoples with type-1 diabetes and patient with other medical illnesses such as heart disease, cancer patient would be excluded from our study.

Discussion: The main purpose of this study is to evaluate the effectiveness of a PSP in improving mental health outcomes among patients with Type 2 diabetes mellitus (T2DM). The program aims to help participants manage depression, reduce diabetes-related distress, enhance social support, improve quality of life (QOL), and increase adherence to treatment. Participants will receive PSP as part of the intervention, and pre- and post-assessments will be conducted to measure changes in psychological well-being and behavioural functioning. This study is expected to **provide** evidence-based guidance for mental health interventions in Type 2 diabetes patients and contribute to better treatment outcomes, supporting both patients and healthcare providers in improving overall well-being.

Trial registration: Trial would be register.

Keywords

Psycho-Social Program, Type 2 Diabetes Mellitus, Depression, *Stigma*, *Social Support*, *Diabetes Quality of Life*, *Treatment Adherence*, *Diabetes Patients*

Administrative information

Trials guidance: please include this text in your submitted protocol just above the Administrative information table:

Note: the numbers in curly brackets in this protocol refer to SPIRIT checklist item numbers. The order of the items has been modified to group similar items (see <http://www.equator-network.org/reporting-guidelines/spirit-2013-statement-defining-standard-protocol-items-for-clinical-trials/>).

Title {1}	
Psycho-social program (PSP) for mental health problems among patients with type 2 diabetes mellitus (T2DM): a randomized control trial.
 
Design. Randomized Control Design
 
Population. Patients with Type II Diabetes
 
Intervention. Psycho-Social Program

Trial registration {2a and 2b}.	Research proposal accepted from the ethical committee and reviews of institution then trial would be register.
Protocol version {3}	Trial would be register.
Funding {4}	This research is not funded.

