Therapist will generate the allocation sequence and would enroll the T2DM diagnosed patients. And then participants would be randomly assign to the experimental and waitlist control group.

Assignment of interventions: Blinding

Who will be blinded {17a}

No one will be blinded after assignment to interventions. At initial of the study, researcher describe the purpose and procedure of the study to the participants and take consent from all participants then researcher would start the study.

Procedure for unblinding if needed {17b}

In this research, researcher and participants would be unblind because the purpose of this to promote and manage their depression, stigma and enhance social support, quality of life and

adherence to treatment. Before, starting the study researcher would take informed consent from all of the patient and give briefing about the study. Then those patients show willingness to take part in the study then research recruit those patients.

Data collection and management

Plans for assessment and collection of outcomes {18a}

Following assessment tools would be used to collect the data from T2DM patients.

Demographic form.

A demographic form will be formed to obtain necessary information about each patient i.e. age of the patient, education, socioeconomic status, and family system, and total family members, marital status, duration of illness, hospital name. This form will be used for further analysis of the result section.

Diabetes Distress Scale (DDS-17 Polonsky, Fisher, Esarles, Hesseler & Mullan 2005).

Diabetes Distress Scale (DDS-17) is used to assess the distress related to diabetes. It consists of 17 items. Each item of the DDS-17 has a six-point Likert scale from 1 (indicating no problem) to 6 (indicating a very serious problem). The total DDS-17 score was calculated by summing a patient's responses to the 17 items and dividing by the number of items on the scale. DM distress was considered clinically significant (moderate distress) if the total score was > 2 , and severe if the score was ≥ 3 . DDS-17 also assesses other components including emotional-related distress, physician-related distress, regimen-related distress, and interpersonal-related distress. Its reliability was reported 0.87 Cronbach's alpha.

The Patient Health Questionnaire (PHQ-9; Ahmad 2018).

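### The baseline chi-square and t-tests in {20a} can neither show nor correct balance between the arms; baseline values should instead be fixed covariates in the between-arm model

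*Protocol*

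**What the plan says.** Statistical methods for primary and secondary outcomes {20a} lists descriptive statistics, then "Chi-square statistics and t-test for matchable group characteristics, and repeated measures ANOVA for pre-and post-outcomes evaluation will be conducted". It gives no significance level, no size of difference that would count as comparable, no action that depends on the test results, and no covariate.

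The Demographic form under {18a} collects "age of the patient, education, socioeconomic status, and family system, and total family members, marital status, duration of illness, hospital name", which is eight items, and says only that the form will serve further analysis.

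The Methods paragraph of the abstract states "Total N=80 diabetic patients would be divided into experimental n=40 and waitlist n=40 participants", and Trial design {8} confirms equal arms. Implementation {16c} says that assignment is random.

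Data management {19} adds a second outcome analysis: "compare the pre and post assessment of the patients through paired sample T-test". That is a pre-post comparison and names no covariate either.

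**The concern.** A significance test on a baseline characteristic asks whether the two arms come from the same population. In a randomised trial the design already answers that. What matters for the outcome comparison is how large the observed gap is and how strongly the characteristic relates to the outcome. A p-value speaks to neither. At 40 per arm a sizeable gap can be non-significant and be taken as reassurance, while a chance p below 0.05 can be taken as a failed randomisation.

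The stake is the handling of characteristics that the trial already collects. Section {20a} gives them a test that cannot do its stated job, and does not give them the use that would help, which is as prespecified covariates in the between-arm comparison.

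**Working it through.** **Inputs.** 40 per arm and 1:1 allocation come from the protocol (abstract Methods; Study setting {9}; Trial design {8}). Assumed, because the protocol does not state them: two-sided 5% level, no dropout, pre-post correlation 0.5, and the correlations of a characteristic with the scores given below. The protocol has no figure of its own on this point to reproduce.

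**1. What the t-test lets through.** The largest non-significant observed gap is t(0.975, 78) × √(2/40) = 1.991 × 0.2236 = 0.445 SD.
- A gap of 0.44 SD gives t = 0.44/0.2236 = 1.97, p = 0.053: passes.
- A gap of 0.50 SD gives t = 0.50/0.2236 = 2.24, p = 0.028: flagged.
- With 36 or 32 per arm (10% or 20% loss) the cut-off rises to 0.470 or 0.500 SD.

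**2. How often such gaps arise under sound randomisation, for one continuous characteristic.** P(|gap| ≥ 0.30 SD) = 18.4% and P(|gap| ≥ 0.445 SD) = 5.0%, so a gap of 0.30 to 0.445 SD that passes the test occurs in about 18.4 − 5.0 = 13.4% of trials. P(|gap| ≥ 0.40 SD) = 7.8%, so a gap just under the cut-off (0.40 to 0.445 SD) occurs in under 3%.

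**3. Chance flags.** If the eight items were independent, P(at least one p < 0.05) = 1 − 0.95^8 = 34% with perfect randomisation. Items such as age and duration of illness are unlikely to be independent, so this is only a rough guide.

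**4. Effect on the planned outcome test.** With one pre and one post score, the group-by-time test of the repeated measures ANOVA is a t-test on change scores. Let a characteristic correlate a with the pre score and b with the post score, and let the arms differ on it by 0.43 SD (t = 1.92, p = 0.058, so it passes). The bias in the change comparison is (b − a) × 0.43 SD. Simulated false-positive rates with no treatment effect (40,000 trials per row, pre-post correlation 0.5):

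| a (pre) | b (post) | Bias in change (SD) | False-positive rate |
|---|---|---|---|
| 0.3 | 0.3 | 0 | 5.1% |
| 0.5 | 0.5 | 0 | 5.0% |
| 0.1 | 0.3 | 0.2 × 0.43 = 0.086 | 6.2% |
| 0.2 | 0.4 | 0.2 × 0.43 = 0.086 | 6.3% |
| 0 | 0.3 | 0.3 × 0.43 = 0.129 | 7.6% |
| 0.1 | 0.4 | 0.3 × 0.43 = 0.129 | 7.7% |

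The excess grows with b − a and with the pre-post correlation. At 0.7, the rows with a difference of 0.2 give about 7% and those with 0.3 about 9.5%. All of these rates are conditional on one particular gap. Averaged over randomisations, the test keeps its 5% level.

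**5. The baseline outcome score.** If the arms differ by 0.44 SD on the pre score itself, the change-score bias is (0.5 − 1) × 0.44 = −0.22 SD. The conditional false-positive rate is 12.4% for the group-by-time test, against 4.9% when the post score is analysed with the pre score as covariate (10,000 simulated trials). Residual variance, in units of the score variance, is 2(1 − 0.5) = 1.00 for change and 1 − 0.5² = 0.75 with the covariate. So covariate adjustment is also more precise, whatever gap occurs.

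**The case against.** The case against has real weight.

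- **A reader might infer that the test misses a 0.5-SD imbalance 40% of the time.** That is the miss rate for a true population difference of 0.5 SD (power 59.8%). Random assignment makes the true difference zero, and an observed 0.5-SD gap at 40 per arm is always flagged (p = 0.028). The 40% would apply only if allocation were subverted. Under {16c} the therapist both generates the sequence and enrols, and {16b} describes no concealment, so this cannot be excluded. That is a separate matter and does not supply a figure here.
- **A reader might infer that unbalanced arms will be declared matched and compared unadjusted.** No rule for declaring arms matched is stated; that purpose is read from the word matchable. The ANOVA also includes the pre score as a time level, so the baseline outcome is not ignored.
- **A reader might put the false-positive rate at 7 to 13%.** That range fits a comparison of post scores alone, with correlations of 0.3 to 0.5. The planned test works on change, where a characteristic related equally to both scores cancels out.
- **Covariates may be named in a statistical analysis plan that is not shown, and {20a} already plans descriptive statistics.** Both are fair. The absence of a covariate list would not be a finding alone. What remains is that {20a} commits to a method for judging comparability that cannot do so.
- **Removing baseline p-values alone changes no result.** This is correct, and it is why the value of the change lies in the covariates.

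**Conclusion.** The point holds as a cheap improvement to the analysis, not as an error that invalidates the trial. The tests in {20a} cannot show that the arms are comparable: at 40 per arm and an assumed two-sided 5% level, every observed gap below 0.445 SD passes, and under sound randomisation a significant result is chance. Nor do they correct anything.

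The cost of leaving the plan as it stands is modest. The group-by-time test keeps its 5% level over all randomisations. In a trial with a 0.43-SD gap on a characteristic, the rate is about 5% if the characteristic relates equally to pre and post scores, and about 6 to 8% if it relates more strongly to post. The latter rests on assumed correlations with the post score of 0.3 to 0.4, exceeding those with the pre score by 0.2 to 0.3, and a pre-post correlation of 0.5. None of these correlations is in the protocol. Fixing covariates in advance is nevertheless the better method, because it deals with whatever gap occurs without depending on a test.

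**What to change.** In {20a}:

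1. Replace the baseline chi-square and t-tests with means, SDs and frequencies by arm, plus standardised differences and no p-values.
2. Analyse each post score between arms with the baseline score of that outcome and one or two characteristics already on the demographic form (for example duration of illness) as covariates.
3. Fix those characteristics before data collection and keep them in the model whatever imbalance is observed.

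The cost is a change of wording and 2 to 3 of about 78 degrees of freedom (leaving 75 or 76). All the data are already planned and SPSS fits the model. The one thing lost is that the report can no longer say the groups were tested and found not to differ at baseline.
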